5.11 Changes to Planned Analyses

Automatic sleep test scoring and manual review of scoring results will not be compared as part of this study analysis. This outcome is the primary focus of the [name] Trial, which will supersede these study results.

6. STATISTICAL SOFTWARE AND QUALITY CONTROL

Day-to-day monitoring of the trial will be carried out by the Oxford Respiratory Trials Unit (ORTU) along with regular data queries and data checks by the trial statisticians.

Data is received by paper Case Report Forms (CRFs) from sites, entered into electronic database by Oxford. Data is held and managed by the ORTU.

All statistical analyses will be generated using SAS® software, version 9.4 or later. Graphics will either be generated using SAS or R software. Statistical analysis will be independently quality checked by a

second statistician to ensure that the SAP has been followed and programming errors are minimized.

7. PLANNED TABLES AND FIGURES

- Number of Subjects Randomized by Treatment Group and Site
- Patient Accountability Flow Chart, Overall and by Analysis Populations
- Reasons for Study Withdrawal by Treatment Group
- Protocol Deviations by Treatment Group
- Demographic and Baseline Characteristics by Treatment Group
- Comparability of Baseline Variables Across Sites
- Pool-ability analysis, Primary Endpoint Results by Site and Treatment Group
- Primary Endpoint Analyses
- Secondary Endpoint Analyses for CC with mild OSA per 2012 AASM Guidelines
- Secondary Endpoint Analyses for CC with mild OSA per 2007 AASM Guidelines
- Adverse Events by Treatment Group
- Secondary Endpoint Analyses for CC with moderate to severe OSA per 2007 AASM Guidelines
- Secondary Endpoint Analyses for CC with no OSA per 2007 AASM Guidelines but who enter the study per AASM 2012 Guidelines.
- Secondary Endpoint Analysis for Patients treated with CPAP comparing Patients Adherent and Non-Adherent to CPAP for CC with mild OSA per 2012 AASM Guidelines
- Secondary Endpoint Analysis for Patients treated with CPAP comparing Patients Adherent and Non-Adherent to CPAP for CC with mild OSA per 2007 AASM Guidelines
- Impact of Baseline Factors on Adherence to CPAP in Treatment Group
- AirView/CPAP Usage Data for Patients treated with CPAP, Overall and Comparing Patients Adherent and Non-Adherent to CPAP
- Number/Percent of Types of Contacts for Patients treated with CPAP, Overall and Comparing Patients Adherent and Non-Adherent to CPAP (+ types of interventions, problems)
- Primary Endpoint Analyses over Baseline AHI, Age, and BMI
- Secondary Endpoint (mean change in ESS and FSS) Analyses over Baseline AHI, Age, and BMI
- Association between Primary Endpoint and ODI and RERA Scores by Treatment Group and CPAP Adherence
- Baseline Demographic Characteristics, AHI, and Quality of Life Scores by Gender
- Secondary Endpoint Analyses by Treatment Group and Gender
- Summary of Change from Baseline in Weight and BMI by Treatment Group
- Primary Endpoint Summarized by Reasons for Patient Referral and Treatment Group

8. AMENDMENT

Amendment to SAP Version 1.4

Effective as of: 19Jun2019

Changes and additions to planned analyses

5.7 – 5.8 Primary and Secondary Endpoint Analyses

SAP version 1.4 specified a mixed-effects repeated measures model as the primary analysis for the

primary endpoint; the primary analysis population was the ITT-1 population. Sensitivity analyses of the primary endpoint, as well as all analyses of secondary endpoints, were also specified using the mixed-effects repeated measures model; the analysis populations of interest were the CC-1 and CC-2 (completed case) populations.

After reviewing preliminary results, the Trial Steering Committee determined that it would be more appropriate to examine endpoints in a true intent-to-treat fashion, including all patients in the analyses, rather than focusing on completed cases.

The primary analysis of the primary endpoint was performed as specified. For sensitivity and secondary endpoint analyses, the mixed-effects repeated measures analysis was replaced with analysis of covariance (ANCOVA) in the ITT-1 and ITT-2 analysis populations. The ANCOVA model adjusted for baseline score, where missing 3-month scores were replaced with baseline scores using a last observation carried forward (LOCF) approach. The advantages of using the ANCOVA LOCF model were (1) it was considered a conservative method of handling missing data, in which patients would have seen no improvement had they remained in the trial, and (2) this approach had the benefit of simplifying the underlying model assumptions.

Secondary endpoints were also analyzed using the ANCOVA LOCF model for the group of patients with no OSA (AHI<5) per **AASM 2007 guidelines** but who entered the study (AHI \geq 5) per **AASM 2012 guidelines**; these patients were considered the “very mild” group.

Additionally, effect sizes were calculated for each analysis model as

$$\text{effect size} = \frac{\text{treatment difference}}{\text{pooled SD}}$$

where

treatment difference = adjusted mean treatment difference (CPAP – SC) from analysis model

pooled SD = $\text{SE}_{\text{trt diff}} / \sqrt{\left(\frac{1}{n_{CPAP}}\right) + \left(\frac{1}{n_{SC}}\right)}$ for mixed effects model

pooled SD = root MSE for ANCOVA LOCF model.

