### 5.5.3 Ongoing monitoring

Participants randomised to the CPAP arm will have their CPAP compliance monitored using the ResMed AirView Remote Monitoring system which accompanies the CPAP devices used in the study (see Section 0.) The Trial Sleep Therapist will be responsible for monitoring all the CPAP data regularly. In order to ensure consistent monitoring and patient follow-up, responsibility of the patient care during the three month study fall to the Trial Sleep Therapist.

The Trial Sleep Therapist will review the data on a regular basis (at least twice per week) and will intervene when compliance is low or other issues are identified. For example, the Trial Sleep Therapist will intervene if they see that for a period of  $\geq 3$  consecutive nights either of the following takes place:

- Compliance is low (<4 hours per night);
- leak is high (>24L/min);
- treatment is not optimal (AHI $\geq 5$ )

In this instance the Trial Sleep Therapist will contact the patient to discuss the issue and potential solutions. Participants will be invited for further clinic visits if required (*CPAP Therapist CRF*). Visits will take place at the participants local sleep service, and will be conducted by the Trial Sleep Therapist. The patient's local sleep service will be informed of any contact and what follow up was taken.

If the participant is unable to be contacted after multiple attempts, the Trial Sleep Therapist will contact the patient's local sleep service and ask for assistance contacting the patient. If contact is still unsuccessful the participant will be withdrawn from the trial and deemed 'lost to follow-up'.

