## 5.6 Control Arm

All participants (including the CPAP group) will be counseled regarding healthy lifestyle behaviors including sleep hygiene habits based on national guidelines and recommendations. Sleep hygiene counseling is considered standard care in this patient group, and many mild patients see an improvement in daytime symptoms when following basic sleep hygiene measures such as spending adequate amounts of time in bed.

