## 5.7 Three month follow up visit

At the end of the 3 month study, participants in both arms will be asked to attend their local sleep service for a three month follow up visit. Participants will be asked to complete the same standardised questionnaires as they completed at the baseline visit (as per Section 10), including the participants weight.

Participants in the CPAP arm will be asked to complete an additional questionnaire regarding their experiences with CPAP and their wish to continue using it (*CPAP Questionnaire CRF*).

At this stage the subject's participation in the trial is complete, and participants will revert to routine clinical practice. **Participants using a CPAP as part of the clinical trial who wish to continue with it will be permitted to keep the CPAP.**

**Participating centres will be provided with sufficient number of CPAPs that patients in the control arm will also have the opportunity to use CPAP at the end of the trial if the patient and their care team feel it is the best option for them.**

In order to select an appropriate study length, similar studies were reviewed. CATNAP found a positive treatment effect from a 2 month trial participation period; however we felt that some patients may need slightly longer to adjust to CPAP therapy. Participants were enrolled in the MOSAIC study for six months; however a study endpoint also included vascular risk. A similar RCT reviewing the effects of treatment on mild OSA had follow up appointments at both three months and six months. The data showed no significant differences in quality of life between the three and six month visits. Therefore, 3 months was considered an appropriate trial length for this study.

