## 11.2 Sample Size calculation

### 11.2.1 Primary Endpoint Calculation

The primary outcome for this evaluation is the Energy and Vitality subscale of the SF-36 questionnaire. Previous clinical trials considering CPAP outcomes in mild OSA patients were reviewed. The MOSAIC study, which has the most similar patient selection criteria, reported an increase in vitality score of 10.8 (SE 1.3) points between baseline and 6 months in the CPAP group, compared with an increase of 4.2 (SE 1.4) in the standard care group. This difference between the treatment groups of 6.6 is considered a significant clinical improvement.

The sample size was calculated using a difference in treatment effect of 6.6 comparing CPAP change between 3 months and baseline (mean change 10.8, SD 17.00) to standard care change between 3 months and baseline (mean change 4.2, SD 18.1) with a 5% significance level and 80% power.

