4.6 Sample Size

The sample size of 224 (112 per arm) is based on statistics observed in the MOSAIC study: a mean score difference of 6.6 was observed between 3 months and baseline (considered a significant clinical improvement by the authors of the study) in the Energy and Vitality subscale of the SF-36 questionnaire, with a mean change of 4.2 (SD 18.1) in the Control group and 10.8 (SD 17.0) in the CPAP Treatment group. The sample size calculation is based on a two-sided 5% significance level and 80% power.

It is estimated that approximately 300 participants will need to be randomised in order to reach the required sample size of 224 patients with mild OSA **per AASM 2012 guidelines**. Subjects who are eligible for Home Sleep Testing (HST) are evaluated for their level of OSA. Those patients who have Mild OSA **per AASM 2007 guidelines** are eligible for randomisation. Those patients who have No OSA **per AASM 2007 guidelines** are further assessed based on the AASM 2012 guidelines. All patients with

AHI \geq 5 per AASM 2012 guidelines are also eligible for randomisation. Since the primary endpoint analysis is based on patients with mild OSA per AASM 2012 guidelines, there will be some patients randomised who will not fall into this sample, thus the need for additional enrolment. Additionally, it is expected that 10% of those randomised will drop-out before the end of the study.

The number of patients required to enrol will be reviewed and updated by the Trial Steering Committee (TSC) as new recruitment information accumulates. This will not change the goal of 224 patients completing the study who had mild OSA per the AASM 2012 guidelines.

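### SAP 1.5 calls baseline-carried-forward ANCOVA conservative for the secondary and sensitivity analyses; that is unproven, because its direction depends on drop-out by arm and on what drop-outs would have scored.

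*SAP*

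**What the plan says.** SAP section 8, effective 19 June 2019, gives the reason for the change: "After reviewing preliminary results, the Trial Steering Committee determined that it would be more appropriate to examine endpoints in a true intent-to-treat fashion". SAP 4.2 expected follow-up to end on 31 March 2019, and version 1.4 was issued on 18 March 2019.

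The primary analysis stays as specified in SAP 5.7. For sensitivity and secondary analyses the mixed model gives way to ANCOVA on ITT-1 and ITT-2: "The ANCOVA model adjusted for baseline score, where missing 3-month scores were replaced with baseline scores using a last observation carried forward (LOCF) approach". Two advantages are claimed. One is simpler model assumptions. The other is that "it was considered a conservative method of handling missing data, in which patients would have seen no improvement had they remained in the trial".

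The group with no OSA by the 2007 rules but AHI of at least 5 by the 2012 rules was to be described only (SAP 5.10). It now receives the same ANCOVA model.

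Both documents expect the control arm to improve. Protocol 11.2.1 takes its planning values from an earlier trial with a CPAP gain of 10.8, "compared with an increase of 4.2 (SE 1.4) in the standard care group". Protocol 5.6 says of sleep hygiene that "many mild patients see an improvement in daytime symptoms when following basic sleep hygiene measures". The only drop-out figure is for the whole trial: "it is expected that 10% of those randomised will drop-out before the end of the study" (SAP 4.6). SAP 5.4 and 5.5 promise missing data and losses by treatment group.

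**The concern.** Each patient has two scores, so carrying the last one forward sets the change to zero for every drop-out in either arm. On CPAP this removes expected benefit. In the control arm it removes expected improvement, which widens the difference in favour of CPAP. Which effect prevails depends on how drop-out splits between the arms, and the plan assumes no split.

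A reader told that the method is conservative will treat a positive secondary result, or a supportive sensitivity result for the primary endpoint, as a lower bound. The plan does not establish that. It matters more because the method was chosen after preliminary results had been reviewed.

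**Working it through.** **Inputs.** Mean change 10.8 (SD 17.0) on CPAP and 4.2 (SD 18.1) in controls, two-sided 5%, 80% power, 112 per arm (Protocol 11.2.1, SAP 4.6); 10% drop-out overall (SAP 4.6); 1:1 allocation (SAP 4.2). Assumed, not in the documents: the split of drop-out by arm, a baseline to 3-month correlation of 0.6 (range 0.5 to 0.7), and drop-out at random within arm. The SAP reports norm-based SF-36 scores and the scale of the planning figures is not stated, so point values assume a shared scale. Ratios, error rates and power do not depend on linear rescaling.

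**Step 1: the plan's own figure.** Pooled SD = √((17.0² + 18.1²)/2) = 17.56. n = 2 × 17.56² × (1.960 + 0.842)² / 6.6² = 111.1, so 112 per arm. The 224 reproduces.

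**Step 2: drop-outs would have changed like completers in their arm.** With pC and pS the drop-out on CPAP and in controls, the carried-forward difference is 10.8(1 − pC) − 4.2(1 − pS). Its bias against 6.6 is 4.2·pS − 10.8·pC, which is positive only if pS/pC > 10.8/4.2 = 2.57. At 10% overall (pC + pS = 20%) the crossover is 5.6%/14.4%.

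**Step 3: CPAP drop-outs would have changed like controls.** The true all-randomised difference is then 10.8(1 − pC) + 4.2·pC − 4.2 = 6.6(1 − pC), and the carried-forward bias is 4.2(pS − pC). If there is no treatment effect and both arms gain 4.2, the bias is again 4.2(pS − pC). The 2.57 ratio plays no part in either case. A MAR analysis estimates 6.6 throughout, so under this assumption it overstates by 6.6·pC.

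| CPAP/control drop-out | Carried forward | Bias, step 2 | Truth, step 3 | Bias, step 3 |
|---|---|---|---|---|
| 15%/5% | 5.19 | −1.41 | 5.61 | −0.42 |
| 10%/10% | 5.94 | −0.66 | 5.94 | 0 |
| 8%/12% | 6.24 | −0.36 | 6.07 | +0.17 |
| 5%/15% | 6.69 | +0.09 | 6.27 | +0.42 |
| 0%/20% | 7.44 | +0.84 | 6.60 | +0.84 |

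**Step 4: standard errors at 10%/10%, correlation 0.6.** The score variance is s² = 17.56²/(2 × 0.4) = 385.4, and the residual variance after baseline adjustment is V = 385.4 × (1 − 0.36) = 246.6.

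- Baseline-adjusted MAR, 100.8 observed per arm: √(2 × 246.6/100.8) = 2.21 (2.22 in simulation).
- Carried forward: the residual variance is 238.0 on CPAP and 229.1 in controls, so SE = √((238.0 + 229.1)/112) = 2.04.
- Mixed model with unconstrained baseline means: √(2[246.6/100.8 + 0.16 × 385.4/112]) = 2.45.

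SAP 4.6 aims for 224 completers, which at 10% drop-out means about 112/0.9 ≈ 124 randomised per arm. The first two become √(2 × 246.6/111.6) = 2.10 and √(467.1/124) = 1.94.

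**Step 5: effect on the test, 112 per arm.** Under no effect the carried-forward SE is about 2.02. At 5%/15% the shift is 0.42/2.02 = 0.21 SE, so the error favouring CPAP is P(Z > 1.96 − 0.21) = 4.0% against 2.5%, and the two-sided error is about 5.5%. Simulation with correlations 0.5 to 0.7 gave 4.0–4.1% and 5.5–5.6%. At 8%/12% the error favouring CPAP is about 3.0%, and at 15%/5% about 1.5%. At the planning effect with 8%/12%, the carried-forward estimate is smaller than 6.6, yet its power is about 86% (6.24/2.04) against about 84% for MAR. A smaller estimate therefore does not guarantee a stricter test.

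**The case against.** The case for the amendment has weight. At planning values, with drop-outs like completers, carrying baseline forward shrinks the estimate at 15%/5%, 10%/10% and 8%/12%, and even at 5%/15% the gain is only 0.09. Null inflation at that split is modest. The intention-to-treat aim is a separate reason for the change.

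MAR is not neutral either. For the CPAP arm, Protocol 5.5.3 says of patients who cannot be reached that "If contact is still unsuccessful the participant will be withdrawn from the trial", and Protocol 5.8 ties benefit to at least 4 hours of use per night. If such patients lose their benefit, carrying baseline forward is exactly right at 10%/10% while MAR overstates by 0.66. This stands, and it is why MAR should be reported beside the carried-forward analysis with that caveat, not in its place.

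Does the protocol indicate which arm will lose more patients? The withdrawal rule in 5.5.3 points to CPAP. Protocol 5.7 gives controls a reason to stay, since "patients in the control arm will also have the opportunity to use CPAP at the end of the trial", but it also lets CPAP participants who wish to continue keep the device. Neither passage gives a rate, so the direction stays open.

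A reader might infer that the committee chose the method because it favoured CPAP. The documents do not support this: they do not say whether the preliminary results were seen by arm. They do not show that the method inflates the effect either.

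The intention-to-treat aim did not require carrying baseline forward. The primary mixed model already runs on ITT-1 with all available data (SAP 5.4, 5.7). The covariate-adjusted sensitivity analysis of SAP 5.7 was also on ITT-1, so the wish to move away from completed cases does not explain replacing it. The amendment names baseline score as the only adjustment, so that analysis appears to have been dropped.

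**Conclusion.** The conservative label is unproven, not always false. For vitality it holds for the point estimate at equal or CPAP-heavy drop-out. If drop-outs resemble completers, it fails only beyond the 2.57 ratio. If there is no true effect, or if CPAP drop-outs resemble controls, it fails at any excess control drop-out. The SE is about 8% smaller than under baseline-adjusted MAR (2.04 against 2.21–2.22, or 1.94 against 2.10), so the test can be less strict even where the estimate shrinks. These sizes rest on the assumed splits and correlation. For the other secondary endpoints the documents give no expected changes, so the direction cannot be computed.

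The consequence is limited. The primary analysis is unchanged, SAP 5.8 declares secondary analyses exploratory, and missing data will be shown by arm. It would be wrong to conclude that the trial's main result is affected.

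**What to change.** 1. For every secondary endpoint, report the mixed model of SAP 5.8, or another baseline-adjusted MAR analysis, on ITT-1 and ITT-2 beside ANCOVA-LOCF. State that the prespecified version used CC-1 and CC-2, that with two visits the ITT version stays close to a completer analysis, and that MAR may overstate the effect if CPAP drop-outs lose their benefit.
2. Label ANCOVA-LOCF, including the model for the very mild group, as chosen after preliminary results, and show missing data by arm next to it.
3. Delete the word conservative, or limit it to endpoints where observed drop-out and change by arm support it.
4. Keep the covariate-adjusted sensitivity analysis of SAP 5.7 on ITT-1 if any baseline variable is found imbalanced.

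The cost is SAP wording and some programming on existing data. Intervals would be about 8–9% wider than under LOCF with baseline adjustment (2.22/2.04, 2.10/1.94), and about 20% wider with unconstrained baseline means (2.45/2.04).

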5.10 Additional Exploratory Analyses

Several of the exploratory analyses did not fit within the scope of the primary manuscript, and will be completed and reported at a later date:

- Summaries and analyses of secondary endpoints in patients with moderate OSA per AASM 2012 guidelines.
- Summaries and analyses of secondary endpoints comparing patients in the CPAP group who are adherent vs. not adherent to treatment.
- Summary of US Medicare definition of adherence.
- Predictors of adherence to CPAP therapy.
- Details of patient contacts.
- Summaries and analyses by gender.

9. DOCUMENT VERSION HISTORY

Version number	Author	Significant changes from previous version
Issue date		
1.0 28Sep2017	[name]	NA
1.2 24Nov2017	[name]	Updates to description of treatment groups, Number enrolled, compliance definition.
1.3 16Nov2018	[name]	SAP recreated following change in trial statisticians.
1.4 18Mar2019	[name]	Updates to subject recruitment dates, definition of HADS summary scores, analysis populations, exploratory analyses and definition of protocol deviations.
1.5 19Jun2019	[name]	Updates to the primary, secondary and exploratory analyses
